# **Study Protocol**

# **Study Design:**

The study is a parallel community-based 2-arm randomized controlled trial (RCT) in which the study evaluations will take place at the Center of Neurorehabilitation (CNR) at Sargent College, Boston University. We will enroll 44 community-dwelling adults ages 40-80 yrs with idiopathic PD of mild to moderate disease severity, who are independent community ambulators. We will exclude those with atypical PD, have significant freezing of gait, have history of falls in the past 3 months, have a comfortable walking speed <0.4 m/s, and significant cognitive or hearing impairments. Eligible participants will be randomly allocated to either

[figure not shown]

Figure 1 Study flow. Abbreviations: CoV: Coefficient of Variation; SAM: Step Activity Monitor; SRHI: Self-Report of Habit Index

Amped-PD (experimental arm) or Active Control (control arm). Assessments will include a standard set of motor and non- motor assessments and will be administered at Baseline, Post-Assessment (after 6 weeks of training), and Follow-up (after 2 additional weeks of unstructured training). Figure 1 summarizes the study flow for the protocol.

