- 1.cRandomization: At the completion of procedures for Baseline Assessment, the participant will be randomized to receive either the experimental or control arm of the intervention. The experimental arm, called Amped-PD, is a 6-week community-based structured walking program that uses a music-adaptive RAS followed by 2 weeks of unstructured walking protocol (continue as desired) for a total of 8 weeks. The control arm, called Active-Control is a similarly structured 6-week community-based walking program that does not use RAS, followed by 2 weeks of unstructured walking protocol (continue as desired) for a total of 8 weeks of training. Block randomization with balanced allocation between the two groups will be implemented. A randomization list will be generated prior to enrollment of participants. The researcher will gain knowledge of treatment assignment only after procedures in In- person Screen and Baseline Assessments have been completed.

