# 3. Second Evaluation Visit: Post-Assessment Visit (approximately 2-3 hours):

The post-intervention assessment visit will be scheduled within approximately 7 days of completion of the structured walking program and take place at the Center for Neurorehabilitation at Boston University. This visit will entail the same battery of assessments performed at Baseline Assessment including: 10MWT, 6MWT, Borg's RPE, Mini BESTest, MDS-UPDRS I/II/III, 5xSTS, PDQ-39, SRHI, GDS. Quantification of movement will be performed using wearable sensors to measure balance and walking as examined in the aforementioned battery of assessments.

Further, a usability questionnaire will be administered for those who completed Amped-PD. For both Amped-PD and Active-Control groups, participants will be asked to bring in their study diary for study personnel to review and to make a copy for their data file. This study diary will be returned to the participant for continued use if needed during the Follow-up Period. For the Amped-PD group, they will have continued access to the music-based device during the Follow-up Period. The SAM monitor will be given to the participant to wear for 7 days during Follow-Up Training. Participants who withdraw or are withdrawn prior to completing their last walking session may be asked to complete closing visit activities, if feasible.

4. Follow-Up Walking Program (2 weeks): Extended Remote Walking Program

Description for both groups (recommended continuation of routine walking + concurrent use of SAM device 4 days during follow-up training)

**Overview:** Participants in both Amped-PD and Active-Control groups will be recommended to carry out the walking program independently for another 2 weeks,

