## **Statistical Analysis Plan**

We will use parametric statistics to data with normal distribution verified using Shapiro-Wilk test and to data that meet the assumptions of homogeneity of variances using Levene's test. Otherwise, non-parametric statistics will be used.

To examine between-group differences for all primary outcomes (moderate intensity minutes, daily steps, stride time variability, and habit strength), we will run a one-way ANOVA or Kruskall-Wallis test to compare change scores at the 6-Week and 8-Week clinical assessments relative to baseline.

To examine within-group differences for all primary outcomes (moderate intensity minutes, daily steps, stride time variability, and habit strength), we will run a Repeated Measures ANOVA or Friedman's ANOVA on absolute values of all primary outcomes across their respective timepoints, with multiple post-hoc comparisons corrected using Bonferroni adjustments.

For all secondary outcomes, we will perform between-group analyses using non-parametric statistics to compare change scores at the 6-Week and 8-Week clinical assessments relative to baseline, using two-tailed tests with alpha set at 0.05.

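### Secondary outcomes are compared on change scores without baseline adjustment: a valid test, but less precise than the collected data allow, and with no planned effect estimate

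*SAP*

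**What the plan says.** The SAP's fourth paragraph covers the secondary outcomes in one sentence: "For all secondary outcomes, we will perform between-group analyses using non-parametric statistics to compare change scores". The comparisons are of "change scores at the 6-Week and 8-Week clinical assessments relative to baseline, using two-tailed tests with alpha set at 0.05". The sentence attaches no distributional condition, names no particular test and includes no covariate, estimate or interval.

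The SAP's opening paragraph sets a general rule: "We will use parametric statistics to data with normal distribution verified using Shapiro-Wilk test", with equal variances also required and non-parametric methods otherwise. The fourth paragraph does not apply that rule and does not say that it is an exception.

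The primary outcomes are also analysed on change and without a covariate: "we will run a one-way ANOVA or Kruskall-Wallis test to compare change scores".

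On size and allocation, the Protocol (Study Design) states: "We will enroll 44 community-dwelling adults ages 40-80 yrs with idiopathic PD". Under Randomization it adds: "Block randomization with balanced allocation between the two groups will be implemented". That paragraph mentions no stratification by a baseline score. Baseline values exist for the measures repeated later; of the post-assessment the Protocol says: "This visit will entail the same battery of assessments performed at Baseline Assessment including: 10MWT, 6MWT". The list there continues with balance, motor, sit-to-stand, quality-of-life, habit and depression measures.

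**The concern.** A change score subtracts the whole baseline value, so it fixes the baseline coefficient at 1. When the correlation between baseline and follow-up is well below 1, this over-corrects and adds noise. Estimating the coefficient from the data removes that noise at the cost of one degree of freedom.

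With 44 participants, precision is scarce. If the secondary outcomes include measures such as walking capacity, balance and motor signs, a moderate real effect is more likely to be missed. As written, the results would also be p-values only. At about 22 per arm, a non-significant p-value without an interval does not tell the reader whether a useful effect has been excluded.

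**Working it through.** **Inputs from the documents.** N = 44 with balanced allocation, taken as 22 per arm; two-sided alpha 0.05; change from baseline at 6 and 8 weeks. The documents give no effect size, SD, power, dropout or correlation, so the figure of 44 cannot be reproduced.

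**Assumptions.** Rho from 0.3 to 0.9; equal SDs at baseline and follow-up; no dropout; a true difference of 0.6 SD for the power figures. The planned test is taken to be a rank test. This is inferred, because the non-parametric tests that the SAP names for the primary outcomes (Kruskal-Wallis, Friedman) are rank tests.

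**Step 1, variance.** In units of the raw variance:
- change score: 2(1 − rho)
- ANCOVA residual: 1 − rho²
- ratio: (1 − rho²) / [2(1 − rho)] = (1 + rho)/2

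For normal data only, the rank test's large-sample efficiency against the t test is 3/pi = 0.955. The combined ratio is then 0.75 × 0.955 = 0.72 at rho 0.5, 0.85 × 0.955 = 0.81 at 0.7 and 0.95 × 0.955 = 0.91 at 0.9.

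**Step 2, detectable difference and equivalent size, normal data.** With 22 per arm and 80% power, the detectable difference is (1.96 + 0.84) × sqrt(2/22) = 0.845 SD of the analysed variable. In raw SD units, multiply by sqrt[2(1 − rho)/0.955] for the rank test on change and by sqrt(1 − rho²) for ANCOVA. At rho 0.5 this gives 0.845 × 1.023 = 0.86 and 0.845 × 0.866 = 0.73. The size per arm at which the rank test matches ANCOVA with 22 is 22 / [0.955 × (1 + rho)/2]. Power was simulated with 20,000 replicates.

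| rho | Variance ratio (1+rho)/2 | Detectable difference, rank on change vs ANCOVA | Rank-test n per arm to match ANCOVA | Simulated power at 0.6 SD, rank on change vs ANCOVA |
|---|---|---|---|---|
| 0.3 | 0.65 | 1.02 vs 0.81 | 35 | 36% vs 52% |
| 0.5 | 0.75 | 0.86 vs 0.73 | 31 | 47% vs 60% |
| 0.7 | 0.85 | 0.67 vs 0.60 | 27 | 68% vs 77% |
| 0.8 | 0.90 | 0.55 vs 0.51 | 26 | 85% vs 89% |
| 0.9 | 0.95 | 0.39 vs 0.37 | 24 | 99% vs 99% |

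Under no effect, the rank test on change rejected in 4.7% to 4.9% of replicates, so it is valid.

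**Step 3, non-normal errors.** Same 22 per arm and 0.6 SD difference, 6,000 replicates, with assumed error shapes:

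| Errors | rho | Rank on change | Linear ANCOVA |
|---|---|---|---|
| Heavy-tailed (t, 3 df) | 0.5 | 62% | 69% |
| Heavy-tailed (t, 3 df) | 0.7 | 85% | 81% |
| Heavy-tailed (t, 3 df) | 0.8 | 96% | 90% |
| Skewed (lognormal) | 0.5 | 75% | 72% |
| Skewed (lognormal) | 0.7 | 96% | 82% |

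The ordering can reverse, so the 0.955 factor and the table in Step 2 do not carry over to skewed or heavy-tailed scales.

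**Step 4, a rank test that adjusts for baseline.** A rank test on residuals from the regression on baseline matched or beat the rank test on change in every shape tried, to within 0.1 percentage point, with type I error of 4.4% to 5.4%. The variant that ranks both outcome and baseline before regressing is slightly worse than the planned test at high correlation with normal data (84.4% vs 84.9% at rho 0.8; 97.6% vs 98.9% at 0.9).

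**The case against.** The best defence is that non-parametric testing suits many of the likely secondary measures. Several are ordinal or bounded scales and one is a timed test. Step 3 shows that a rank test on change can have clearly more power than linear ANCOVA with such errors. This stands, and it rules out a linear model as the main analysis for every scale. It does not defend leaving baseline unadjusted, because the rank method in Step 4 keeps the robustness and uses baseline as a covariate.

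A second defence is that a specific clause may override a general one, and that fixing the test in advance avoids choosing it by a normality pretest in a small sample. This also stands. The mismatch between the opening and fourth paragraphs is a wording matter to be reconciled, not an error in itself.

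A reader might draw stronger conclusions that the documents do not support:
- *Baseline information is thrown away.* It is not; a change score uses it with a fixed coefficient.
- *Chance imbalance is a separate bias.* With 22 per arm the baseline difference has a standard error of sqrt(2/22) = 0.30 SD. An imbalance of 0.3 SD shifts the change contrast by (1 − rho) × 0.3, or 0.15 SD at rho 0.5 and 0.09 SD at 0.7. That variation is already inside the ratio (1 + rho)/2, and randomisation keeps the comparison unbiased.
- *A rank test rules out an estimate in scale units.* A Hodges-Lehmann shift with interval can accompany it; the SAP simply plans none.
- *Power is lost for no benefit.* Robustness is a real benefit.
- *The sponsor presents the choice as conservative.* Neither document says so.

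**Conclusion.** The point holds as one of precision and reporting, not validity. For roughly normal measures, adjustment would reduce variance to about 0.75 of the change-score value at rho 0.5 and 0.85 at rho 0.7, which matters in a trial of 44. At rho 0.8 or above the gain is small. These sizes rest on assumed correlations, equal SDs and no dropout; the power figures also assume a 0.6 SD effect. The additional loss from ranking applies only to normal data.

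Two limits of scope apply. Neither document lists the secondary outcomes, so the examples are taken from the repeated battery less the named primaries. The absence of a covariate and of a planned estimate applies equally to the primary outcomes; only the unconditional non-parametric choice is particular to the secondary ones.

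**What to change.** Revise the SAP's fourth paragraph before the data are analysed:

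1. List the secondary outcomes, and adjust each comparison at 6 and 8 weeks for that outcome's baseline value.
2. For ordinal, bounded or skewed scales, use a rank-based ANCOVA, for example a rank test on baseline-adjusted residuals. For approximately continuous measures such as walking speed and 6MWT distance, use a linear model with arm and baseline.
3. Assign each outcome to its method in advance, not by a normality pretest, and state how this relates to the rule in the opening paragraph.
4. If robust standard errors are used, specify a small-sample version (HC3). In a normal null simulation at rho 0.7, the uncorrected version (HC0) with a normal reference gave 6.7% type I error, against 4.5% for HC3. HC3 costs some power: at rho 0.9 and a 0.35 SD difference, it and the planned test both had 70%.
5. Report the between-arm difference with 95% CI beside each p-value, as an adjusted mean difference or a Hodges-Lehmann shift.

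The cost is SAP wording and slightly more analysis work. For measures in the repeated battery, no visit or measurement is added.
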